#### 7.2.4.6.1 Hematology

Hematology samples will be collected during the core phase at Screening Visits 1 and 2, Visit 3, 5 - 16 and 777 (EOT) and will be sent to the central laboratory, **[Egypt: Local laboratory]**. During the optional extension phase, hematology samples will be collected every 3 months as per Exjade prescribing information. Hematology parameters monitored during the study are listed in [Table 7-4](#).

#### 7.2.4.6.2 Clinical chemistry

Clinical chemistry samples will be collected during the core phase at Screening Visits 1 and 2, at Visit 3, 5-16, and 777 (EOT) and will be sent to the central laboratory, **[Egypt: Local laboratory]**. During the optional extension phase, monthly assessments will be done as per Exjade prescribing information as per [Table 7-2](#). Patients who were on the DT arm during core phase of study and decided to switch to granules as part of the optional extension phase will need to return weekly for the first month of the optional extension phase at Visits 18, 19 and 20 for serum creatinine and creatinine clearance monitoring. Thereafter they will follow the same schedule as patients who were on granules arm during the core phase. Clinical chemistry parameters to be measured are listed in [Table 7-4](#).

In accordance with the deferasirox label, serum creatinine, creatinine clearance, alkaline phosphatase, ALT/SGPT, AST/SGOT, direct (conjugated) bilirubin, indirect bilirubin, total bilirubin must be assessed in duplicate before the initiation of therapy to establish a reliable pre-treatment baseline.

In addition, serum creatinine will be measured weekly during the first three weeks (after the first study drug administration and at Visits 4, 5) and monthly thereafter (starting with Visit 6) till Visit 777 (EOT). During the optional extension phase, monthly assessments will be done as per Exjade prescribing information for patients previously on the granules arm of the core phase. Patients on the DT arm for the core phase of the study who have decided to switch to granules as part of the optional extension phase will need to return weekly for the first month at Visits

18, 19 and 20. Creatinine clearance will be calculated by the central lab **[Egypt: Local laboratory]** using the Schwartz formula for patients 17 years and younger and the Cockcroft-Gault formula for patients who turn 18 years old during the study, each time serum creatinine is collected.

#### 7.2.4.6.3 Urinalysis

Urinalysis samples will be collected during the core phase at every study visit, from Screening until Visit 777 (EOT). During the optional extension phase, monthly assessments will be done as per Exjade prescribing information. A midstream, second voided morning urine sample will be obtained as this will provide the best results. Urinalysis parameters assessed are listed in **Table 7-4**.

The microscopic urinalysis will be performed only in case of positive dipstick. Dipsticks will be supplied by the central lab, **[Egypt: Local laboratory]**.

At Screening Visits 1 and 2, a urine sample (at least 15 ml) will be collected and sent to the central lab **[Egypt: Local laboratory]** for urinary protein/creatinine (UPC) ratio to assess the eligibility of the patient. Thereafter UPC ratio will be assessed at every visit, till EOT, as described in the **[Central Laboratory Manual]**, **[Egypt: Local Laboratory Manual]**. First morning void samples must not be used for this analysis.

For patients who develop proteinuria or a worsening of pre-existing proteinuria (assessed by a dipstick) at any visit, please refer to **Table 6-2**.

#### 7.2.4.6.4 Pregnancy and assessments of fertility

Females of child-bearing potential are defined as all females physiologically capable of becoming pregnant. This includes female pediatric patients who are menarchal or who become menarchal during the study.

All menarchal girls and their parents/caregivers should be informed about the potential risks of pregnancy and the need to prevent pregnancy during the study. It is important to be sensitive in introducing this issue, as understanding and comprehension of puberty, sexual activity, pregnancy and contraception is influenced by age, as well as factors such as precocity, socio (educational) economic and familial background. These discussions with the patient and her parents/caregivers are therefore best performed by investigators familiar with the pediatric subject and her family and should be guided by requirements of the local regulatory authorities. These discussions should take into account the socio-economic, cultural factors and religious beliefs of the adolescent participant and her family.

The investigator should also discuss the management of the pregnancy test results with the patient and her parents/caregivers. The privacy of the patient should be considered in accordance with the local law and ethics.

Serum and/or urine pregnancy tests will be performed for all females of child-bearing potential according to the schedule in **Table 7-1** for the core phase. Urine pregnancy tests will be at the EOT visit (777) and then at Investigator's discretion during the optional extension phase treatment period as per schedule in **Table 7-2**. Urine pregnancy tests will also be performed at

the end of treatment in the extension phase as per Novartis guidelines for pregnancy testing in clinical trials when basic contraception is requested.

Additional pregnancy tests may be performed at the investigator's discretion during the study. Patients becoming pregnant or breastfeeding must be discontinued from study drug.

However, a patient may choose to remain in the study should she become pregnant, and be followed according to the protocol-defined study visits.

Female patients of child-bearing potential, who are or might become sexually active, must be informed of the need to prevent pregnancy during the study.

The basic contraception methods are:

- Barrier method: Condom or Occlusive cap (diaphragm or cervical/vault caps). [For UK: with spermicidal foam/gel/film/cream/vaginal suppository].
- Placement of an intrauterine device (IUD) or intrauterine system (IUS).

The decision on the contraceptive method should be reviewed at least every 3 months to evaluate the individual need and compatibility of the method chosen.

Please note that deferasirox may reduce the efficacy of hormonal contraception thus it is recommended to use alternative methods of contraception as described above.

See [Section 8.4](#) for pregnancy reporting and follow-up requirements.

#### 7.2.4.6.5 Hepatitis Viral tests

Hepatitis Viral testing consists of the following items: Hepatitis B Surface Antibody (Anti-HBs), Hepatitis B core Antibody (HbcAb), Hepatitis C Antibody (Anti-HCV), Hepatitis B surface Antigen (HBsAg), Qualitative w/confirmation, HCV PCR (Quantitative). Hepatitis Viral testing will be conducted at Screening Visit 1 (core phase) to assess trial eligibility.

#### 7.2.4.7 Cardiac assessments

[figure not shown]
##### 7.2.4.7.1 Electrocardiogram (ECG)

A standard 12 lead ECG will be performed and interpreted by site personnel during the core phase at the following visits:

- at screening Visit 1
- at visit 777 (EOT)

During the optional extension phase, ECG will be performed when clinically indicated.

Interpretation of the tracing must be made by a qualified physician and documented on the ECG CRF page. Each ECG tracing should be labeled with the study number, patient's initials (where regulations permit), patient number, date and kept in the source documents at the study site. Clinically significant abnormalities present when the patient signed informed consent should be reported on the Medical History eCRF page. Clinically significant findings must be discussed with Novartis prior to enrolling the patient in the study. New or worsened clinically significant findings occurring after informed consent must be recorded on the Adverse Events eCRF page.

#### 7.2.4.7.2 Echocardiography

A standard echocardiogram will be performed and interpreted by the site personnel during the core phase at the following visits:

- at screening Visit 1
- at visit 777 (EOT)

During the optional extension phase, echocardiography assessments will be done when clinically indicated.

Interpretation of the echocardiogram must be made by a qualified physician and documented on the CRF page. Each echocardiography should be labeled with the study number, patient's initials (where regulations permit), patient number, date and kept in the source documents at the study site. Clinically significant abnormalities present when the patient signed informed consent should be reported on the Medical History eCRF page. Clinically significant findings must be discussed with Novartis prior to enrolling the patient in the study. New or worsened clinically significant findings occurring after informed consent must be recorded on the Adverse Events eCRF page.

#### 7.2.4.8 Growth and Development

##### 7.2.4.8.1 Growth velocity assessment in pediatric patients

At the end of core phase, the growth velocity will be assessed from the difference between the end of-core phase and the baseline height measurements during the core phase.

During the optional extension phase, growth assessment will be performed annually as per Exjade prescribing information.

##### 7.2.4.8.2 Pubertal stage

Pubertal stage will be scored at baseline and end of core phase according to Tanner staging system.

During the optional extension phase, pubertal stage assessment will be performed annually as per Exjade prescribing information.

#### 7.2.5 Pharmacokinetics

Detailed instructions for the collection, handling, and shipment of PK samples will be presented in the [\[CICL670F2202 Pharmacokinetics Laboratory Manual\]](#). PK sampling will only be performed during the core phase.

#### 7.2.5.1 PK blood sample collection and handling

##### 7.2.5.1.1 Blood collection plan

PK blood samples will be collected in all patients **[Egypt: no PK samples will be collected]** at weeks 1, 3, 5, 9, 13, 17, 21, 25, 29, 33, 37, 41 and 45 visits to support the assessment of compliance (see [Table 7-5](#)). Patients / caregivers will be instructed that study drug should not be administered in the morning of these visits.

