Objective	Endpoint	Analysis
To evaluate pre-dose PK data to support the assessment of compliance	Pre-dose deferasirox concentrations in all patients [except Egypt] at Weeks 1, 3, 5, 9, 13, 17, 21, 25, 29, 33, 37, 41 and 45 visits(13 samples)	Refer to Section 10.5.6.1
Post-dose data to be analyzed along with pre-dose PK data	Post-dose deferasirox concentrations between 2 and 4 hours post-dose at Weeks 5 and 9 (2 samples)	Refer to Section 10.5.6.2
To explore exposure-response relationships for measures of safety and effectiveness	Serum creatinine change from baseline, notable serum creatinine event, serum creatinine clearance change from baseline and notable serum creatinine clearance events, urine protein creatinine ratio change from baseline and serum ferritin change from baseline, in relationship to pre- and post-dose deferasirox concentrations.	Refer to Section 10.5.6.3
Secondary (Optional Extension phase)		
To assess additional safety data about new formulation (granules) in pediatric population	Overall safety, as measured by frequency and severity of adverse events (including active monitoring for renal toxicity; including renal failure, hepatic toxicity; including hepatic failure, and gastrointestinal hemorrhage), and changes in laboratory values from baseline (serum creatinine, creatinine clearance, ALT, AST, RBC and WBC). In addition, vital signs, physical, ophthalmological, audiometric, and growth and development evaluations will be assessed.	Refer to Section 10.5.4 and Section 10.6.1

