**Table 7-5 PK blood collection log (all patients)**

Visit	Week	Day	Scheduled time point	PK collection number	PK Sample No	Sample volume [mL]
3	1	1	Pre-dose	1	1	2
5	3	1	Pre-dose	2	102	6***
6	5	1	Pre-dose	3	103	7
6	5	1	Post-dose 3 hour (+/- 1 hour)	3	9	2
7	9	1	Pre-dose	4	104	12
7	9	1	Post-dose 3 hour (+/- 1 hour)*	4	13	2
8	13	1	Pre-dose	5	105	14
9	17	1	Pre-dose	6	106	15
10	21	1	Pre-dose	7	107	16
11	25	1	Pre-dose	8	108	17
12	29	1	Pre-dose	9	109	18
13	33	1	Pre-dose	10	110	19
14	37	1	Pre-dose	11	111	20
15	41	1	Pre-dose	12	112	21
16	45	1	Pre-dose	13	113	22
999	Unscheduled**	--		--	1001+	2
		Total				30

PK collection numbers 1 to 13 correspond to the dose taken on the day of the visit.

PK collection numbers 102 to 113 correspond to the dose taken the day before each study visit.

\*One PK blood sample should be collected between 2 and 4 hours post-dose

\*\* Each unscheduled PK blood sample will be uniquely numbered with sample number 100X (e.g., 1001, 1002, etc.) and will add 2 mL of blood to the total quantity collected

\*\*\* Certain PK samples have been removed as part of Protocol Amendment V.01 so PK sample numbers are no longer consecutive. Please follow numbering convention in [Table 7-5](#).

On the days of visit 6 (Week 5) and visit 7 (Week 9) deferasirox should be administered at the study site under supervision of the investigator/site staff. This is to ensure appropriate draws of pre- and post-dose administration blood samples for PK assessments.

At Week 1, the pre-dose sample should be obtained before the first drug administration. At Week 5 and Week 9, the pre-dose PK sample should be obtained within  $24 \pm 2$  hours from the previous dose, and one post-dose PK sample should be obtained between 2 and 4 hours post-dose administration.

The time of all blood draws will be recorded on the PK blood collection page in the eCRF. All samples will be taken by either direct venipuncture or indwelling cannula inserted in a forearm vein.

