### **2.9.1.3 Compliance diary**

The Compliance questionnaire consists of 2 items. Item 1 assessed whether the medication was taken (yes/no) and Item 2 is a record of the time when the medication was taken with a not applicable option for patients who did not take their ICT.

The daily compliance questionnaire diary records will also be used to calculate the rate of dose violations. For a given day, a dose violation is defined as a dose that is either missed completely or not taken in accordance with the timing instruction (no later than 12:00 pm). The dose violation rate is calculated as:

$$[\text{Number of dose violations} / \text{Drug exposure (days)}] * 100$$

Weekly average of dose violation rate will be calculated and summarized using descriptive statistics by treatment arm, type of questionnaire (ObsRO questionnaire versus PRO questionnaire) and week (weeks 1, 13, 25, 37 and core EOT). Additionally, absolute change from week 1 will be tabulated including 95% confidence intervals for mean. A graphical representation will be provided over all week periods by treatment arm and type of questionnaire. The y-axis will be the mean and SD and the x-axis will be the corresponding week period (see [Table 4-3](#) for week periods definition).

Due to the use of ePRO there will be no individual items missing. The weekly average rates will be calculated when there are at least four non missing daily responses. For a given week the denominator will be the number of non-missing days. No additional imputation will be carried out.

The number of patients completing the compliance diary and the number of expected and missing days will be summarized by each treatment arm and type of questionnaire for the FAS-3.

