**Table 4-3 Week periods for compliance diaries**

Week Period	Week Period Definition
Week 1 period	Study Day 1 – 7
Week 2 period	Study Days 8 – 14
Week 3 period	Study Days 15 – 21
Week $y$ period (with $y=4, 5, 6, \dots$ )	Study Days $(y-1)*7+1$ to $y*7$
Etc.	
Study Day 1 = first day of study treatment	

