### 2.9.5.3 Compliance diary

The Compliance questionnaire consists of 2 items. Item 1 assessed whether the medication was taken (yes/no) and Item 2 is a record of the time when the medication was taken with a not applicable option for patients who did not take their ICT.

The daily compliance questionnaire diary records will also be used to calculate the rate of dose violations. For a given day, a dose violation is defined as a dose that is either missed completely or not taken in accordance with the timing instruction (no later than 12:00 pm). The dose violation rate is calculated as:

$$[\text{Number of dose violations} / \text{Drug exposure (days)}] * 100$$

Weekly average of dose violation rate will be calculated and summarized using descriptive statistics by treatment arm, type of questionnaire (ObsRO questionnaire versus PRO questionnaire) and week (weeks 1, 13, 25, 37 and core EOT). Additionally, absolute change from week 1 will be tabulated including 95% confidence intervals for mean. A graphical representation will be provided over all week periods by treatment arm and type of questionnaire. The y-axis will be the mean and SD and the x-axis will be the corresponding week period (see [Table 4-3](#) for week periods definition).

Due to the use of ePRO there will be no individual items missing. The weekly average rates will be calculated when there are at least four non missing daily responses. For a given week the denominator will be the number of non-missing days. No additional imputation will be carried out.

The number of patients completing the compliance diary and the number of expected and missing days will be summarized by each treatment arm and type of questionnaire for the FAS-3.

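### Diary scoring has no exemption for PK visit days or the first dose, so doses the visit procedure pushes past noon can count as violations in the tabulated weeks

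*Protocol*

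**What the plan says.** Protocol 7.2.5.1.1 schedules pre-dose samples "at weeks 1, 3, 5, 9, 13, 17, 21, 25, 29, 33, 37, 41 and 45 visits to support the assessment of compliance", in all patients except those in Egypt. It adds that on those days "study drug should not be administered in the morning of these visits". Below Table 7-5, weeks 5 and 9 get a further instruction: "On the days of visit 6 (Week 5) and visit 7 (Week 9) deferasirox should be administered at the study site under supervision".

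SAP 2.9.1.3 (Amendment 3) defines a diary violation as "a dose that is either missed completely or not taken in accordance with the timing instruction (no later than 12:00 pm"). The weekly rate is summarised by arm, questionnaire type "and week (weeks 1, 13, 25, 37 and core EOT"), and plotted over all weeks. A weekly rate needs at least four completed diary days and uses the completed days as its denominator. End of Core Phase SAP 2.9.5.3 repeats the definition and the weeks, and both SAPs plan the same contrast: "Additionally, absolute change from week 1 will be tabulated including 95% confidence intervals for mean".

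Protocol 7.2.3 and 10.5.5 use a looser rule: the dose is missed, or not taken at roughly the same time each day. None of these sections exempts PK days.

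**The concern.** Diary compliance is a named secondary objective. Protocol 2.2 wants several adherence measures because pill counts overstate adherence. A family that follows the PK-day instruction literally cannot also meet a noon limit, so the plan can record obedience to one of its own rules as a breach of another.

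The affected days fall in the four numbered weeks chosen for the table, including the week 1 reference. Core EOT is free of them. The change from week 1 to EOT, with its confidence interval, can then show better adherence when behaviour has not changed.

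**Working it through.** No power or sample-size figure is involved. I read 12:00 pm as noon.

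**Number of affected visits.** The list in Protocol 7.2.5.1.1 has 13 entries, which agrees with Table 3-1. As a check, 13 pre-dose plus 2 post-dose samples at 2 mL each give 15 × 2 = 30 mL, the total in Table 7-5. Over 48 weeks that is 13/336 = 3.9% of dosing days.

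**Where the visits fall in the diary.** Visits are timed from randomization (Protocol 7.1). Assuming the first dose is on that day, a week-w visit held on schedule is study day (w − 1) × 7 + 1. SAP Table 4-3 starts diary week w on the same day:

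- week 1: day 1, diary days 1–7
- week 13: day 85, diary days 85–91
- week 25: day 169, diary days 169–175
- week 37: day 253, diary days 253–259

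Neither Protocol 7.2.5.1.1, Table 3-1 nor Table 7-5 lists a draw at core EOT. The core visit schedule (Table 7-1) is not in the text available to me, so the absence of an EOT draw rests on those three places.

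**Visit window.** Visits after Visit 6 may move by ±7 days, which is 15 allowed days. The PK day stays in its diary week only for shifts of 0 to +6 days, or 7 of the 15.

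**Week 1.** Protocol 6.4.2 and SAP 4.1.1 place first dispensing at randomization, and the week 1 sample precedes the first dose. The day-1 dose therefore waits for the visit in every patient. In Egypt, where no PK sample is taken, it still waits for randomization and dispensing.

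**Size for a fully adherent child.** One late dose in m completed diary days gives 1/m: 14.3% for m = 7, 16.7% for 6, 20.0% for 5 and 25.0% for 4.

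**Size at an assumed true daily violation rate p.** With seven diary days and one forced violation, the weekly rate is (1 + 6p)/7. The spurious change from week 1 to EOT is p − (1 + 6p)/7 = −(1 − p)/7.

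| Assumed p | Rate in an affected week | Spurious change, week 1 to EOT |
|---|---|---|
| 0% | 14.3% | −14.3 points |
| 5% | 18.6% | −13.6 points |
| 10% | 22.9% | −12.9 points |
| 20% | 31.4% | −11.4 points |
| 30% | 40.0% | −10.0 points |

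**Other contrasts.** Changes from week 1 to weeks 13, 25 and 37 largely cancel, because both ends hold one affected day when the visit is on time. With one forced day in both arms, a true arm difference in such a week shrinks by 6/7, so 10 points becomes 8.6.

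**The case against.** The strongest reply is that the instruction only means holding the dose until the draw. The surrounding text supports this. SAP 2.2 counts a pre-dose sample as evaluable at 24 ± 4 hours after the previous dose, and the protocol asks for 24 ± 2 hours at weeks 5 and 9. A child who doses at 8:00, the protocol's own example, has an evaluable draw by noon at the latest, and by 10:00 at weeks 5 and 9. If the dose follows at once, the noon rule may never be triggered. This stands, and it is why the lower end of the range is zero.

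The visit window also stands as a limit, as does the descriptive, secondary status of the endpoint.

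A reader might infer more than the documents support:

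- **That the week 1 to EOT change would come only from the missing PK draw at EOT.** The day-1 delay arises from randomization and first dispensing and would occur without any PK sample.
- **That Egyptian patients are free of the problem.** They are free of it at weeks 13, 25 and 37, but not on day 1.
- **That the protocol's same-time rule creates the same conflict.** It gives no tolerance, and its example takes the first dose as the reference time, so a forced violation is not shown. The clear conflict is with the noon limit, which appears only in the SAPs.
- **That one formulation is favoured.** DT is taken fasting and granules may be taken with a light meal, so delays could differ between arms. The documents give nothing to size this, and the PK schedule is the same in both.

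**Conclusion.** The conflict holds between the PK-day instruction and the SAP's noon rule. For a fully adherent child, the excess in a tabulated week is 0 to 14.3 percentage points with seven diary days and up to 25 points with four. The upper end assumes that the visit falls in its diary week and that the dose is taken after noon. The zero at EOT assumes no PK day in the EOT week, which could fail for a patient who stops treatment close to a PK visit.

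The distortion lies in the level of the weekly rates, the week 1 to EOT change and the plot over weeks. The co-primary stick pack and tablet count is not affected. The problem is worth correcting because the remedy is cheap, but it does not threaten the trial's main conclusions.

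**What to change.** Change the analysis only. On study day 1 for all patients, and on any day with a pre-dose sample recorded on the PK eCRF page, count a violation only if the dose was missed completely and ignore its timing. Keep the day in the denominator, so that the four-day minimum works as now and a missed dose on that day still counts. Using actual sample dates also handles shifted visits.

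Report this as the diary rate, or as a sensitivity table beside the existing one. The final-analysis SAP does not plan to repeat the diary analysis, so a sensitivity table or a caveat beside the End of Core Phase results would suffice. The End of Core Phase SAP already has a table of changes to protocol-specified analyses in which such a rule could be recorded.

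The cost is one derivation rule using dates already collected. The PK-day dosing instruction and the diary timing rule must be reconciled in the documents; no dosing instruction is proposed here.
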